one of three trained CM staff will turnover during the project's first two phases, each center will be required to identify one or more replacement CM staff. Thus, if one of the initially trained CM staff withdraws from the study for any reason during the Preparation or Implementation phase, a replacement CM staff will be immediately trained.

- c. *Community-based OUD treatment center patients (Patients).* Each center will agree to deliver CM to all patients newly admitted over a 6-month period. In addition, each center will be asked to enroll approximately one eligible CM patient per week to complete research assessment measures. Eligible patients will be: a) adult patients, b) newly admitted to the opioid treatment center within the past 30 days, and c) prescribed any FDA-approved OUD medication. To optimize ecological validity, exclusion criteria will be minimal and will only include issues that could interfere with the ability to complete a brief intake interview including acute intoxication, acute psychosis, acute mania, or cognitive impairment (prohibiting comprehension of the consent process), as reported by opioid treatment center staff or observed by research staff. We focus on newly admitted patients as opposed to those established in treatment because the need is highest among these patients: drop-out rates and missed doses are higher during the first 6 months of treatment (i.e., the "induction phase") than any subsequent period.

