- c. *Patient assessments.* Patients will complete assessments at baseline and at 3 and 6 months post-intake. Brief baseline assessments will be conducted by research staff either in person at the participating centers or via phone. Multiple strategies will be used to prevent attrition. At baseline, multiple sources of contact information will be recorded for patients. Contact information will be updated by periodic phone calls. In addition, patients will provide detailed contact information of two friends or family members ("locators") who can be contacted if research staff is unable to reach them. Reminders will be made via phone, text, and email: the reminders will not contain any details about the study and will simply note a reminder about an upcoming appointment. Patients who cannot be reached over the phone for follow-up will be identified as needing follow-up from the designated outreach team, who will attempt in-person contact in at the patient's home or OUD center. Patients will receive a slightly escalating schedule of compensation in the form of a Clincard, a reloadable Mastercard card for completing the baseline (\$20), 3-month (\$20), and 6-month follow-up (\$25) assessments. Our analysis plan assumes 80% completion of patient follow-up assessments.

- d. *Electronic medical record (EMR)*. All 30 sites have agreed to document CM session delivery in their medical records (using the Post-Session Self-Report Form) and to extract patient data into an online Qualtrics template created for this project (using the Medical Record Data Extraction Form). Providers will enter session data into the Post-Session Self-Report Form in the medical record. Data will be extracted from the medical record from staff at the participating opioid treatment centers at two timepoints: a) end of 9-month Implementation phase and b) end of 12-month Sustainment phase.

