 - iii. **CM Sustainment**. This is a patient-level measure of the number of CM sessions delivered per patient during the 12-month Sustainment phase. Using the same protocol as for CM Exposure, data will be extracted at the end of the Sustainment phase from 25 randomly selected patients meeting eligibility criteria (i.e., newly admitted to OUD pharmacotherapy during the Sustainment phase; 25 patients * 30 sites = 750 patients). A continuous measure of the number of sessions received, as counted by the number of Medical Record Data Extraction forms completed, will be created for each patient.

b. *Patient outcomes.* Our **Secondary Aim** tests the effectiveness of the two implementation conditions (ATTC vs. E-ATTC) on two patient outcomes: Opioid Abstinence and Opioid-Related Problems.

- i. **Opioid Abstinence.** Patient abstinence from opioids will be assessed via 3- and 6-month post-baseline interviews, during which patients will self-report days of abstinence using the Timeline Followback (TLFB).²⁰ Abstinence will be corroborated via dip urine screens from Redwood Toxicology testing for: heroin/opiates, oxycontin, benzodiazepines, cocaine, methamphetamines, and THC. In addition, at the request of participating centers, single-panel screens will test for fentanyl, a highly lethal opioid not detected in multi-panel screens. A urine screen negative for all opioids (heroin/opiates, oxycontin, fentanyl) will be required for coding of 90 days abstinence. Other drug use detected via the TLFB or urine will be examined as covariates in the analysis.
- ii. **Opioid-Related Problems.** Opioid-related problems will be assessed via patient self-report at 3- and 6-months post-baseline using the Substance Problem Index,²¹ which is a count of DSM symptoms experienced by the patient (range from 0 to 11). Both Drs. [name] and [name] have successfully used this index²²⁻²⁴ in prior studies. The index will be tailored to focus specifically on problems due to opioids.

c. *Putative mediators.* Our **Exploratory Aim** tests putative mediators of implementation outcomes: implementation climate and leadership engagement. Organization-level scoring is described in **Analytic Plan**. The putative mediator scales are measured at the start of the Preparation phase and the midpoint of the Implementation phase.

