- i. **Implementation climate.** A 6-item measure of CM staff and leadership shared perceptions regarding the extent to which the innovation being implemented (i.e., CM) is expected, supported, and rewarded within their center.²⁵ Each item is scored on a 5-point Likert scale. This well-validated, brief measure was developed by Jacobs and colleagues, and following published guidelines, we calculate a scale mean for each staff member.
- ii. **Leadership engagement.** A 4-item measure of CM staff and leadership shared perceptions regarding the extent to which leadership is committed to, involved in, engaged in, and accountable for the implementation of the innovation (i.e., CM). Each item is scored on a 5-point Likert scale. Developed and validated as part of [name] current NIDA-funded project, this measure has demonstrated excellent internal reliability ($\alpha = .94$) and has been shown to be a significant predictor of staff-level implementation fidelity ($\beta = .18, p < .05$).²⁶

d. *Covariates.* We measure potential baseline covariates at the patient, staff, and organization level. These measures are only administered at baseline. Specific measures used include:

- i. **Baseline organization form.** A form measuring baseline characteristics including years of operation, number of patients served, and medications prescribed.
- ii. **Implementation Readiness.** A well-validated 12-item pragmatic measure developed by Shea and colleagues²⁷ will assess readiness to implement CM.
- iii. **CM Attitudes.** A brief measure of attitudes towards CM, as well as providers' perception of its effectiveness and acceptability will be administered. This measure was developed by the NIDA Clinical Trials Network and has been used in multiple NIDA funded studies.
- iv. **Provider demographics.** At the provider-level, we measure staff tenure, education level, and attitudes towards CM.

- v. Patient demographics. At the patient-level, we measure biological sex, race/ethnicity, age, and problem severity.
- vi. Patient clinical characteristics. At baseline, we administer a general measure of global health functioning. This scale was developed by the NIH funded patient-reported outcomes study and is used in multiple NIH funded studies.
- e. *Other Measures*. As noted in prior sections, we also collect some additional measures.

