- b. For the **Primary and Secondary Aims**, we test a series of multilevel models in which patients (Level 1) are embed within staff (Level 2) and within centers (Level 3). Consistent with Raudenbush and Bryk's multilevel modeling approach,³² the proportion of variance to-be-explained at each level will be examined as an initial step. Next, following a decomposed-first strategy that advocates for starting with moderation-focused hypotheses to avoid biases associated with conflated effects,³³ we conduct multilevel regressions testing the extent to which our covariates significantly moderate the hypothesized relationship between condition and outcome. We test covariates at three levels: organizational (e.g., years of operation, number of patients, medications prescribed, implementation readiness), staff (e.g., tenure, education, CM attitudes), and patient (e.g., age, race, biological sex, problem severity). If moderation is not found, covariates will be controlled for as predictors. Condition assignment (ATTC vs. E-ATTC) will be the primary independent measure of interest for analyses. In addition to reporting statistical significance, we will report the effect size (ES) using Cohen's d .³⁴
- c. For the **Exploratory Aim**, we again test a series of 3-level models. For each mediator, the average correlation within group (r_{wg}) will be computed to determine whether aggregation of staff level responses to the organizational-level is warranted. Values of r_{wg} range from -1.00 to 1.00, with values $\geq .60$ representing acceptable agreement.³⁵ Centers with r_{wg} values $< .60$ will be excluded from analysis. Exploratory analyses will apply a Baron and Kenny³⁶ style mediation approach,

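### No baseline count of opioid-abstinent days is listed, so Opioid Abstinence, one of two secondary patient outcomes, cannot be adjusted for its own starting value

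*Combined protocol and SAP*

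**What the plan says.** Item 9.b.i of the combined protocol and SAP defines the outcome and its timing: "Patient abstinence from opioids will be assessed via 3- and 6-month post-baseline interviews, during which patients will self-report days of abstinence". The instrument is the Timeline Followback, corroborated by urine screens. Item 9.b.ii schedules the Substance Problem Index at the same two follow-up points.

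A baseline interview does exist. Item 8.c states: "Patients will complete assessments at baseline and at 3 and 6 months post-intake". Its analytic content has to be read from the covariate list in item 9.d. For patients that list gives: "At the patient-level, we measure biological sex, race/ethnicity, age, and problem severity". It adds: "At baseline, we administer a general measure of global health functioning". No instrument is named for problem severity, and days of opioid use or abstinence are not mentioned.

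Item 10.b tests covariates first as moderators. Then: "If moderation is not found, covariates will be controlled for as predictors". Its patient-level entry reads "patient (e.g., age, race, biological sex, problem severity", an open list of examples without baseline abstinence.

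Centers are the randomized unit, with urn balancing on number of patients served and percent receiving methadone (item 2). Patients enter by a consent-to-contact form handed out at the front desk (item 4.c). They are eligible if "newly admitted to the opioid treatment center within the past 30 days" (item 3.c).

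**The concern.** Patients are not individually randomized. The order of the phases suggests that they enroll after their center's condition is fixed; this is an inference, since the documents do not state it. About 25 of an expected 102 new patients per center enroll, by voluntary consent, so the enrolled group could differ between conditions in opioid use at entry. One arm-specific influence is visible: in E-ATTC only, providers earn $200 for each patient who receives 10 or more CM sessions (item 7.b), and exposure is extracted for the enrolled patients (item 9.a.i). The documents do not say that this shapes enrollment. Without a measure of opioid use at entry, however, the sponsor could not check directly whether it did.

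Two lesser losses follow. The outcome model forgoes a covariate that could sharpen the comparison. The multiple imputation in item 10.a, which must cover the roughly 20% of follow-ups expected to be missing, lacks a natural predictor.

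**Working it through.** **The plan's own figures.** 30 centers x 25 patients = 750, as stated. With 80% follow-up, 0.80 x 25 = 20 patients per center and 600 in all. The documents give no power statement, effect size, SD or ICC, so there is nothing further to reproduce.

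**Assumptions, not from the documents.** 15 centers per arm; center ICC 0.05 to 0.10; correlation r between baseline and follow-up abstinence 0.3 to 0.5. Units are patient-level SDs.

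**Step 1. Chance imbalance at baseline.** With 25 enrolled per center, the SD of the difference between arms is sqrt(2 x DE / 375), where DE = 1 + 24 x ICC.
- ICC 0.05: DE = 2.20, SD = 0.108, 95% range +/-0.21.
- ICC 0.10: DE = 3.40, SD = 0.135, 95% range +/-0.26.

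This variation is already part of the standard error of a correctly clustered model. It is not a bias on top of it.

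**Step 2. Precision gain if only patient-level variance is explained.** The variance of a center mean is ICC + (1 - ICC)/20. The covariate multiplies the second term by 1 - r², which is 0.91 or 0.75.
- ICC 0.05: 0.0500 + 0.0475 = 0.0975. With r = 0.3 it becomes 0.0932 and the SE falls by 1 - sqrt(0.0932/0.0975) = 2.2%. With r = 0.5 it becomes 0.0856 and the SE falls by 6.3%.
- ICC 0.10: 0.1000 + 0.0450 = 0.1450. With r = 0.3 it becomes 0.1410 and the SE falls by 1.4%. With r = 0.5 it becomes 0.1338 and the SE falls by 4.0%.

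**Step 3. Precision gain if center-level variance is explained in the same proportion.** The SE falls by 1 - sqrt(1 - r²), which is 4.6% for r = 0.3 and 13.4% for r = 0.5. At ICC 0.05, the difference detectable with 80% power (two-sided 5%) moves from 0.32 SD to 0.31 SD (r = 0.3) or 0.28 SD (r = 0.5).

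**Step 4. What the planned covariates already recover.** Take, as an illustration only, a difference of 0.2 SD in baseline abstinence. At r = 0.5 it shifts the contrast by 0.5 x 0.2 = 0.10 SD. Suppose problem severity correlates q with baseline abstinence and acts only through it. The shift left after adjusting for severity is 0.10 x (1 - q²): 0.09 SD for q = 0.3 and 0.05 SD for q = 0.7. Adjustment is therefore partial, and how partial depends on an instrument that is not named.

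**Step 5. Whether another listed variable fills the gap.** Item 9.b.i says that other drug use found by Timeline Followback or urine will be examined as a covariate. The only time points listed for those sources are 3 and 6 months. Measured then, the variable follows allocation, so adjusting for it could remove part of the effect.

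**The case against.** The strongest reply is that random allocation of centers permits a valid comparison of follow-up levels without any baseline value. That stands as far as chance imbalance is concerned. A reader might infer from the 95% limits in Step 1 that 0.07 to 0.14 SD of bias enters the contrast (about 0.2 to 0.3 SD times r). The documents do not support this: those are extreme chance values that the clustered standard error already covers. Randomizing centers does not, however, protect against differential enrollment of patients after allocation.

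A reader might also infer that starting differences cannot be corrected at all. They can in part, because problem severity, demographics and global health are measured at baseline and planned as predictors. Nor is Opioid Abstinence the main patient outcome: the two patient outcomes are unranked, both are secondary, and the primary implementation outcomes are untouched.

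Finally, not listed is not the same as not collected. The covariate lists are open. Item 9.d also says of its covariates: "These measures are only administered at baseline". Set beside the Timeline Followback covariate in item 9.b.i, this leaves some ambiguity. The supported statement is that no baseline abstinence measure is specified. If one is collected, the plan should say so and state its use.

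Two limits on the benefit also stand. The correlation of 0.3 to 0.5 is assumed. How well use before admission predicts abstinence among newly admitted patients on medication cannot be learned from the documents.

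**Conclusion.** The point holds in a limited form. No baseline count of abstinent days is specified, so Opioid Abstinence cannot be adjusted for its own baseline as the plan is written. The precision cost is small to moderate: about 1% to 6% of the standard error if the covariate works at patient level only, and up to about 13% if it works equally at center level, under the assumed ICC and correlation. The stronger reason to act is differential enrollment. The documents neither show that it occurs nor allow its size to be estimated, and they list no baseline measure of opioid use with which to look for it. The change is worth making but does not threaten the trial's primary aim.

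**What to change.** - Add the opioid Timeline Followback to the baseline interview, with a stated look-back window that ends at center admission rather than at the interview. Patients may enroll up to 30 days after admission, when CM may already have begun. The window should match the follow-up window in length; the abstinence coding rule in item 9.b.i implies 90 days.
- Pre-specify baseline abstinent days as a fixed covariate in the Opioid Abstinence model and as a predictor in the multiple imputation.
- Name the problem-severity instrument. For the Opioid-Related Problems model, use the opioid-tailored Substance Problem Index for the pre-admission period as that covariate.
- Report both baseline values by condition, so that differential enrollment can be seen. Adjustment would correct it only in part, since enrolled patients may also differ in ways not measured.
- If these measures are already taken at baseline, state this in items 8.c and 9.d.

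Both instruments are already in the study, and the baseline interview is already held and paid for ($20 per patient, item 8.c). The cost is a somewhat longer interview, in an assessment that the plan intends to keep brief, and recall of a period that ended up to 30 days earlier.

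### Other drug use found at the 3- and 6-month visits appears to be a covariate for Opioid Abstinence; adjusting for it could move the condition effect away from the total effect of assignment

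*Combined protocol and SAP*

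**What the plan says.** Section 9b.i defines the outcome and its timing: "Patient abstinence from opioids will be assessed via 3- and 6-month post-baseline interviews". Abstinent days come from the TLFB. Dip urine screens corroborate them, and the panel also covers benzodiazepines, cocaine, methamphetamines and THC. The paragraph ends: "Other drug use detected via the TLFB or urine will be examined as covariates in the analysis".

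Section 9d describes the covariates as baseline measures and says "These measures are only administered at baseline". For patients it states "At the patient-level, we measure biological sex, race/ethnicity, age, and problem severity", and it adds a measure of global health functioning. Other drug use is not listed.

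Section 10b tests covariates as moderators of the condition effect, and then: "If moderation is not found, covariates will be controlled for as predictors". Its patient covariates are given only as examples; other drug use is neither named nor excluded. The same section makes condition assignment the independent variable of main interest and promises Cohen's d. Section 10a commits to intent-to-treat.

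On visits, Section 8c says "Patients will complete assessments at baseline and at 3 and 6 months post-intake". It calls the baseline assessment brief and does not itemise it. No section describes a baseline TLFB or urine screen.

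**The concern.** On the natural reading, the covariate in 9b.i is drug use found at the outcome visits. That is after centers were randomized and after contingency management (CM) can have acted: Section 5 allows up to 12 weeks of prize draws, so a course begun at intake would be over by the 3-month interview.

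A covariate measured then may itself be changed by condition. If it is also associated with abstinent days, conditioning on it removes or adds part of the effect the secondary hypothesis is about. The association need not be causal; an unmeasured cause shared by both kinds of drug use is enough. Cohen's d taken from that model would carry the same difference. Using the variable as a moderator does not avoid the problem, because the condition effect is then still estimated conditional on a variable measured after assignment.

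The wording also leaves it open, after the data are seen, whether the adjusted or the unadjusted result is the main one.

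**Working it through.** **Reading the sections together.** The instruments named in 9b.i are described only at 3 and 6 months. Section 9d's baseline-only sentence governs the measures listed there, and other drug use is not one of them. Section 10b's default gives any covariate that does not moderate a place in the model. Nothing keeps follow-up drug use out of the main model or limits it to a sensitivity analysis. So either 9b.i adds a follow-up covariate outside the baseline rule, or it means a baseline measure that is not described.

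**Size.** The plan gives no effect size, SD or ICC for abstinence, so there is no figure to reproduce. What follows is an illustration.

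*From the documents:* 30 centers, 25 patients per center, and "Our analysis plan assumes 80% completion of patient follow-up assessments". Hence 30 × 25 × 0.80 = 600 patients followed, or 20 per center.

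*Assumed:*
- equal split (15 centers and 300 followed patients per arm)
- shift *a* in other drug use due to condition: -0.2 to +0.2 SD
- within-condition slope *b* of abstinent days on other drug use: 0 to -0.4 SD per SD
- ICC 0.01 to 0.10
- within-patient correlation *r* between visits: 0.5 to 1.0 (*r* = 1 is equivalent to one visit)

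*Step 1: difference between the adjusted and total effect.* Adjusted minus total = -(*a* × *b*).
- *a* = -0.2, *b* = -0.4: -(0.08) = -0.08 SD
- *a* = +0.2, *b* = -0.4: +0.08 SD
- *a* = ±0.2, *b* = -0.2: ±0.04 SD
- *a* = 0 or *b* = 0: 0

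*Step 2: standard error of the condition effect, averaging two visits.* SE = √(2 × [ICC/15 + (1 - ICC) × ((1 + *r*)/2)/300]).

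| ICC | SE, *r* = 0.5 | SE, *r* = 1 | 0.08/SE, *r* = 0.5 | 0.08/SE, *r* = 1 |
|---|---|---|---|---|
| 0.01 | 0.079 | 0.089 | 1.01 | 0.90 |
| 0.05 | 0.107 | 0.114 | 0.75 | 0.70 |
| 0.10 | 0.134 | 0.139 | 0.60 | 0.58 |

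*Step 3: simulation with clustering* (30 centers × 20 patients, ICC 0.05, *b* = -0.3, 2000 runs per case).
- Total effect 0.30; *a* = -0.2, 0, +0.2: mean adjusted estimates 0.24, 0.30, 0.36. These hold both when the slope is causal and when it comes only from a shared unmeasured cause.
- Total effect 0.05, *a* = -0.2: -0.015 (causal) and -0.010 (shared cause); the formula gives 0.05 - 0.06 = -0.01.
- Total effect 0, *a* = -0.2: about -0.06.
- *b* = 0, *a* = -0.2: adjusted and unadjusted agree (0.31 and 0.31).

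*Step 4: precision given up by leaving the variable out, if condition does not affect it.* Proportional reduction in SE from including it, single visit: 1 - √([ICC/15 + (1 - ICC - *b*²)/300] / [ICC/15 + (1 - ICC)/300]). This runs from 0.7% (ICC 0.10, *b* = -0.2) to 7.0% (ICC 0.01, *b* = -0.4). If the same *b*² is removed from a two-visit average with *r* = 0.5, the upper end is about 9%.

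**The case against.** The best defence is Section 9d. It is the plan's one general statement on covariates, it is baseline-only, and the examples in 10b largely match its list. On that view the rule in 10b covers only the 9d set, and being examined in 9b.i does not mean being controlled for in the main model. It stands that entry into the model is not certain. But the 9d sentence speaks of the measures it lists, the 10b list is open, and 9b.i explicitly calls other drug use a covariate. The result is a conflict between sections that 9d does not resolve.

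Second, the assumed shift may be generous. Both arms are trained to offer CM to all new patients, and Section 5 rewards compliance with treatment contacts, not abstinence from other drugs. Any effect of condition on cocaine, THC or benzodiazepine use would be indirect. That is fair, and the range includes zero for this reason. The figure of about 1.0 standard error needs the largest shift, steepest slope, smallest ICC and lowest *r* together. At ICC 0.05 with *a* = ±0.2 and *b* = -0.3, the difference is 0.06/0.114 to 0.06/0.107, or about 0.5 to 0.6 of a standard error.

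Third, the sentence does not say which analysis it means, so it is unstated whether the Opioid-Related Problems model is included. That adds to the need for clarification.

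**Conclusion.** The concern holds in conditional form. The plan names as a covariate a variable it describes only at the outcome visits, and its default rule could carry that variable into the main abstinence model. The text does not settle whether it does.

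Harm requires three things: the variable enters the model, condition shifts it, and it is associated with abstinent days. If all three hold, the condition coefficient and Cohen's d no longer describe the total effect of assignment. Under the assumed ranges the difference is at most 0.08 SD either way, and its sign depends on the direction of the shift. Within those ranges it can reverse the sign of the estimated effect only when the total effect is smaller than 0.08 SD. The true size and direction cannot be derived from the documents.

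The sentence sits under one secondary outcome; the primary implementation outcomes are not affected. It should be fixed because the repair is nearly free. Confidence is medium, given the loose wording of 9b.i.

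**What to change.** State in Sections 9b.i and 10b that the main abstinence models adjust only for baseline covariates. State that other drug use found at 3 or 6 months will be reported as a separate outcome or in an analysis labelled exploratory, and will be neither a predictor nor a moderator in the main model. Say whether the same rule applies to Opioid-Related Problems.

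If baseline drug use was intended, say so in 9b.i and list the measure and its instrument in 9d.

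The main change is wording only and needs no new data. Its cost is the precision in step 4: if condition does not affect other drug use, including it would have made the standard error about 1% to 7% smaller (up to about 9% for two visits at *r* = 0.5). A baseline measure, if wanted and not already collected, would lengthen a baseline interview planned to be brief.
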